9.2 Subject Accountability

The number of subjects screened, randomized to IP, receiving IP, and completing the study will be summarized. Study discontinuation and IP discontinuation will be tabulated separately by reasons for discontinuation, **including due to COVID-19 Impact if applicable**. The number of subjects included in and excluded from each analysis set and reason for exclusion will also be summarized.

Key study dates for the first subject enrolled, last subject enrolled, last subject's end of IP and last subject's end of study will be presented.

The number and percentage of subjects randomized will be tabulated by study site.

9.3 Important Protocol Deviations

Important Protocol Deviations (IPDs) categories are defined by the study team before the first subject's initial visit and updated during the IPD reviews throughout the study prior to database lock. These definitions of IPD categories, subcategory codes, and descriptions will be used during the study. Eligibility deviations are defined in the protocol.

The number of subjects reporting Protocol Deviations due to COVID-19 Impact will be summarized in a table. A Protocol Deviation listing of subjects impacted due to COVID-19 Impact will also be provided.

9.4 Demographic and Baseline Characteristics

All baseline tables will be summarized by randomized treatment group and for all subjects in the FAS. Baseline tables will summarize the following (but not limited to): baseline characteristics, demographics, cardiovascular medical history, and **lipid** parameters. Difference in stratum assignment between randomized stratum and data-derived stratum will be tabulated.

9.5 Efficacy Analyses

Endpoint	Primary Analysis	Sensitivity Analysis	Multiplicity Adjustment
Primary Endpoint			To preserve the family wise type 1 error rate at 0.05 for testing the primary and secondary endpoints, the primary analysis of primary endpoint will be tested first. If the treatment effect from the primary analysis of the primary endpoint is significant at a two-sided significance level of 0.05, the secondary endpoints will be tested with two-sided significance level of 0.05 using the Hochberg method.
Absolute change in minimum FCT from baseline to week 50	Multiple Imputation + ANCOVA (FAS)	Quade Test (FAS) COVID-19 Impact Analysis	
Secondary Endpoints			
Coronary artery based: 
 Percent change in minimum FCT in a matched segment of the artery as determined by OCT from baseline to week 50. Absolute change in mean minimum FCT for all images accessed in an individual subject as determined by OCT from baseline to week 50. Absolute change in the maximum lipid arc in a matched segment of artery as determined by OCT from baseline to week 50. Plaque-based: 
 Absolute change in minimum FCT, maximum lipid arc, and lipid core length in lipid rich plaques defined as minimum FCT < 120µm 	Multiple imputation + ANCOVA (FAS)	NA	

9.5.1 Analyses of Primary Efficacy Endpoint(s)

Primary Analysis:

To assess the primary endpoint of absolute change in minimum FCT from baseline to week 50, an ANCOVA (Analysis of Covariance) model on the FAS will be used, including terms for treatment group, stratification factor (current statin use [> 4 weeks or ≤ 4 weeks] at screening), baseline minimum FCT as covariates. Least square means and corresponding 95% confidence intervals (CI) will be calculated for each treatment group and for the difference between treatment groups. For subjects with missing post-baseline **minimum FCT**, the **post-baseline minimum FCT value** will be imputed

using multiple imputation. The imputation model will include treatment group, stratification factor, baseline LDL-C, baseline minimum FCT, age as covariates. **At least** five imputations will be conducted, and each complete dataset after imputation will be analyzed using the ANCOVA model. SAS PROC MIANALYZE will be used to combine the results from individual ANCOVA models.

Sensitivity Analysis

- 1) Non-parametric analysis (Quade test) will be performed on FAS as sensitivity analysis. The missing data will be imputed using multiple imputation. **The imputation model and the analysis approach of combining results from multiple imputed datasets will be same as the primary analysis.**
- 2) **COVID-19 Impact sensitivity analysis:**
To determine the impact of COVID-19, a sensitivity analyses will be conducted. All the available post-baseline FCT values will be considered in the analysis, irrespective of the analysis visit window (ie, the post-baseline FCT values after week 56 will also be considered for the analysis). The ANCOVA model for COVID-19 Impact analysis will include the covariates of treatment group, stratification factor (current statin use [> 4 weeks or ≤ 4 weeks] at screening), baseline minimum FCT as covariates. The imputation method, model and analysis approach will be same as the primary analysis.

Covariate and Subgroup Analysis

In addition to the primary analysis, covariate adjusted analysis of the primary efficacy endpoint will be performed as supportive analyses using the baseline covariates in [Section 4.1](#), in their original format, one at a time, in the ANCOVA model used in the primary analysis.

Subgroup analyses on the primary efficacy endpoint will be conducted using the subgroups specified in [Section 4.2](#), in the ANCOVA model used in the primary analysis. Subgroup by treatment interactions will be tested and the p-value of the interaction term will be reported.

For covariate and subgroup analyses, the data-derived stratification factor from the CRF will be used.

Supplementary Analysis:

The following additional analyses will also be performed to evaluate the robustness of the primary analysis result:

- The primary analysis will be repeated using OAS
- The primary analysis will be repeated using CAS

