3.2 Sample Size

The planned total sample size is 150 subjects (75 randomized to evolocumab 420 mg SC QM and 75 randomized to placebo SC QM). This sample size will provide sufficient power (90%) to determine whether there is a treatment effect of evolocumab relative to placebo in the primary endpoint.

The assumptions in the sample size calculation are based on a linear regression meta-analysis of 7 historical trials ([Dai et al, 2017](#); [Hou et al, 2016](#); [Kataoka et al, 2014](#); [Komukai et al, 2014](#); [Nishio et al, 2014](#); [Hattori et al, 2012](#); [Takarada et al, 2009](#)) weighted by sample sizes.

The analysis result indicates that every 1 mg/dL reduction in LDL-C is estimated to be associated with 1.4785 μm increase in FCT in 12-month follow-up. Assuming a 50 mg/dL reduction in LDL-C, the predicted mean increase (95% CI) in FCT from the meta-analysis was 73.92 (50.97, 96.88) μm. For this study, the assumed treatment effect is at least 50.97 μm increase in FCT, which is approximated from the lower bound 95% CI of the expected change in FCT from the regression model, based on a conservative assumption of 50 mg/dL reduction in LDL-C from baseline to week 50.

The SD of FCT measurement at baseline or at the end of various length of follow-up was reported in a wide range (10.6 to 124 μm) based on 15 to 134 subjects per arm in the historical trials. The SD of change in FCT was only reported in 2 of the 7 trials, ranging from 22 to 86 μm. The assumed common SD for this study is 86 μm to be conservative.

Assuming 1 out of 6 subjects will not complete both baseline and week 50 OCT assessments, and therefore be excluded in the primary analysis, the sample size of 150 subjects will provide approximately 125 subjects in the primary analysis to ensure 90% power to test the study hypothesis.

The sample size calculation was performed using a 2-sided t-test with a 0.05 significance level. The sample size calculation was derived using East® software (version 6.4).

4. Covariates and Subgroups

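### Adding baseline LDL-C and age to the primary ANCOVA would be a cheap, modest precision gain; leaving them out is not an error

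*SAP*

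**What the plan says.** SAP 9.5.1 and protocol 10.3.2.2 agree on the primary model: an ANCOVA on the full analysis set with treatment group, statin-use stratum (more than 4 weeks, or 4 weeks or less) and baseline minimum FCT. Missing week-50 values are multiply imputed from a larger set of terms (SAP 9.5.1): "The imputation model will include treatment group, stratification factor, baseline LDL-C, baseline minimum FCT, age as covariates".

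SAP 4.1 lists age, sex, baseline LDL-C, type 2 diabetes and tobacco use as planned covariates. SAP 9.5.1 uses them in supportive models, "in their original format, one at a time, in the ANCOVA model used in the primary analysis". Secondary endpoints follow the primary method with their own baseline value (SAP 9.5.2).

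Both variables should be available for essentially every randomized subject. LDL-C at screening is an entry criterion (protocol 6.1, criterion 104), and SAP 5.3 takes baseline LDL-C from that local sample. Age is recorded at enrollment (SAP 5.3).

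The sample size (SAP 3.2, protocol 10.1) rests on a regression across 7 historical trials, in which "every 1 mg/dL reduction in LDL-C is estimated to be associated with" a 1.4785 µm gain in FCT.

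**The concern.** A baseline variable that predicts the outcome within arms tightens the treatment estimate when it enters the analysis model. Four statements in the documents together make baseline LDL-C a plausible predictor of FCT change:

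- The screening LDL-C sample should be taken between admission and the angiogram (protocol 9.1.1).
- Statin therapy is then started or raised to the maximally tolerated dose in both arms before randomization (protocol 7.1.4), so the baseline value may precede intensified background treatment.
- Evolocumab's effect is reported as a percentage fall, seen regardless of baseline LDL-C (protocol 3.3.1.1, 3.3.1.2). A roughly constant percentage means a larger absolute fall from a higher start.
- The plan ties LDL-C fall to FCT gain (SAP 3.2).

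For age, the only support is that the team chose it as a predictor in the imputation model.

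At stake is the width of the primary interval. The primary test also gates all six secondary endpoints (SAP 2.1, 9.1), so a small gain in precision has some further value.

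**Working it through.** **1. The plan's own figure.** Inputs from SAP 3.2: "The sample size calculation was performed using a 2-sided t-test with a 0.05 significance level"; "the assumed treatment effect is at least 50.97" µm; "The assumed common SD for this study is 86" µm; 150 randomized 1:1; 1 in 6 not evaluable.

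- Evaluable: 150 × 5/6 = 125.
- SE of the difference: 86 × √(4/125) = 15.38 µm.
- Power (noncentral t, 123 df): 90.8%.
- The t-test needs 122 evaluable for 90%, and 122/(5/6) = 146.4, so 147 randomized.

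The plan's 150 and 90% reproduce. The calculation is unadjusted, so it does not depend on any covariate.

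**2. Effect of added covariates.** Let R² be the share of remaining outcome variance that LDL-C and age explain. The SE is multiplied by √(1 − R²). The documents give no R², so the values below are assumed. Power is measured from the unadjusted t-test at 125 observed, and the loss of two degrees of freedom is ignored.

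| Assumed R² | SE (µm) | SE reduction | Power |
|---|---|---|---|
| 0 | 15.38 | – | 90.8% |
| 0.01 | 15.31 | 0.5% | 91.0% |
| 0.02 | 15.23 | 1.0% | 91.3% |
| 0.05 | 14.99 | 2.5% | 92.1% |
| 0.10 | 14.59 | 5.1% | 93.4% |

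**3. Is 1-10% reasonable for LDL-C?** This is an illustration only. Suppose the trial-level slope held between subjects and each subject's fall were proportional to baseline. With a common slope in both arms,

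R² = (1.4785 × mean fractional fall × SD of baseline LDL-C)² / 86².

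Assumptions: a 60% fall on evolocumab (the order reported in protocol 3.3.1.1), 0-30% on placebo, and a baseline SD of 20-40 mg/dL. The last two are not in the documents.

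- Low end: mean fall (0.60 + 0)/2 = 0.30, SD 20. 1.4785 × 0.30 × 20 = 8.87; 8.87²/7396 = 0.011.
- High end: mean fall (0.60 + 0.30)/2 = 0.45, SD 40. 1.4785 × 0.45 × 40 = 26.6; 26.6²/7396 = 0.096.

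These are marginal values. The model already holds the statin-use stratum, and the LDL-C entry floors differ by statin use (130, 80 and 60 mg/dL), so the two overlap. If the stratum explained an assumed 20-60% of LDL-C variance, the range would shrink to about 0.011 × 0.4 = 0.004 up to 0.096 × 0.8 = 0.077. No comparable calculation is possible for age.

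**4. Does imputation already capture the gain?** Simulation: 150 randomized, one sixth missing at random, covariate always in the imputation model, 2,500 runs, stratum and baseline FCT left out for simplicity. Adding the covariate to the analysis model cut the mean SE from 15.48 to 15.19 µm at R² 0.05 (1.9%) and from 15.36 to 14.73 µm at R² 0.10 (4.1%). Using the covariate in the imputation model alone does not deliver the gain.

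**The case against.** The case for leaving the model alone is strong, and much of it stands.

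- **The sample-size regression does not promise this gain.** A reader might infer that the plan's own LDL-FCT relation says the precision is there to take. It does not. The slope concerns on-study LDL-C reduction, estimated across 7 trials. It has no coefficient for baseline LDL-C, is not a within-arm subject-level model, and is silent on age.
- **The richer imputation model is not a defect.** A reader might infer that the imputation and analysis models must match. Auxiliary variables in the imputation step are ordinary practice, and nothing here turns on a mismatch.
- **Power is adequate without the change.** The plan states: "This sample size will provide sufficient power (90%) to determine whether there is a treatment effect". That reproduces from an unadjusted test. The planned ANCOVA already adjusts for baseline FCT and stratum. If those explained an assumed 10% of variance, power would already be 93.4%, and a further 2% or 5% of the remainder would give 93.8% or 94.5%. The percentage reduction in SE is therefore the fairer measure of the gain.
- **Each covariate is already in a supportive model.** Only joint adjustment, and adjustment in the primary analysis itself, are absent.
- **The change is not quite free.** Protocol 10.3.2.2 names the three-term model, and SAP Section 10 declares no changes from the protocol.

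What this does not remove is that two baseline variables, already collected and already judged useful for predicting the outcome, are left out of the analysis that decides the trial.

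**Conclusion.** This is an optional efficiency improvement. The documents show no bias, type I error problem or shortfall in power. Under an assumed further 1-10% of variance explained beyond stratum and baseline FCT, the SE falls by about 0.5-5%. Measured from the unadjusted 90.8%, power becomes about 91-93%. Overlap between LDL-C and the statin stratum makes the lower part of that range more credible. The LDL-C contribution rests on a plausible chain of reasoning plus assumed inputs. The age contribution rests only on the team's choice of imputation terms.

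**What to change.** Before unblinding, amend SAP 9.5.1 so that the primary ANCOVA contains treatment, statin-use stratum, baseline minimum FCT, baseline LDL-C and age. Amend SAP 9.5.2 so that each secondary model contains treatment, stratum, its own baseline value, baseline LDL-C and age. Keep the three-term protocol model as a named supportive analysis. Replace the no-changes statement in SAP Section 10 with an entry recording the departure from protocol 10.3.2.2 and the reason for it.

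If the team prefers to leave the protocol-specified primary model untouched, the minimum step is one pre-specified supportive model with both covariates. That would show the joint adjustment but would not tighten the primary estimate.

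Cost: two of about 120 degrees of freedom, no new data, and a declared change to the protocol-specified primary and secondary models.

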6.2 OCT Analysis Set (OAS)

The OCT analysis set includes subjects in the FAS with a baseline **FCT** and an **FCT** measurement conducted on or after week 40.

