9.5.3 Analyses of Exploratory Efficacy Endpoint(s)

The exploratory endpoints will be analyzed using ANCOVA. The model will include change or percent change from baseline for each exploratory endpoint as dependent variable, and terms for treatment group, stratification factor (current statin use [> 4 weeks or ≤ 4 weeks] at screening) and corresponding baseline values as covariates. The p-values displayed will be considered as descriptive. The analysis will be carried out on observed data and missing data will not be imputed.

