9.6.5 Exposure to Concomitant Medication

The number and proportion of subjects receiving medications of interest (MOI) will be summarized by preferred term or category for each treatment group as coded by the World Health Organization Drug (WHODRUG) dictionary. **Statin intensity will be summarized by treatment group at each targeted scheduled visit date.**

10. Changes From Protocol-specified Analyses

There are no changes to the protocol-specified analyses.

11. Literature Citations / References

12. Appendices

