Appendix A. Analytical Study Week Assignments

Selected endpoints will be summarized by scheduled study visits in descriptive analyses. Since the actual visits may not exactly coincide with their scheduled visit day, the actual visit day is mapped to the study visit generally by non-overlapping consecutive intervals covering the entire time continuum. The mapping intervals for all distinct schedules are summarized in the following table:

Analytical Study Week	Screening	Day 1	Week 4	Week 24	Week 50
Scheduled Visit Day		1	29	169	351
Physical Examination	[-7, 1)	1			> 176
Vital Signs	[-7, 1)	1			> 176
Fasting Lipid Testing		1		(1, 259]	> 259
OCT	[-7, 1)				(280, 393]
IVUS	[-7, 1)				(280, 393]
Biomarker collection (blood/plasma)					> 176
Statin Therapy	[-7, 1)	1	29	169	351

Handling multiple records assigned to an analytical study week:

If there is more than one record in a study week interval, the analytical record for that specific study week will be defined as the record closest to the scheduled visit day of that specific study week ($7 \times \text{study week} + 1$). If two records are equidistant from the scheduled day, then the earlier record will be chosen. If there are multiple records on the same day, the last record will be used.

Concomitant medication records will be selected when the start day or end day equal to the scheduled visit day, or the concomitant medication usage time period includes the scheduled visit day.

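### Does the SAP leave open whether an OCT scan after week 56 counts as observed or missing in the primary and secondary analyses?

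*SAP*

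**What the plan says.** **Primary analysis.** The table in SAP section 9.5 gives "Multiple Imputation + ANCOVA (FAS") for the primary endpoint, the change in minimum FCT to week 50. Sections 8.3 and 9.5.1 impute a missing post-baseline FCT and name no time window. Section 9.5.2 carries the method over to the six secondary endpoints.

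**COVID-19 sensitivity analysis (section 9.5.1).** It uses every available follow-up FCT value, "irrespective of the analysis visit window (ie, the post-baseline FCT values after week 56 will also be considered for the analysis".

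**Visit windows (Appendix A).** OCT and IVUS map to week 50 when the study day lies in (280, 393]. The introduction reads "Selected endpoints will be summarized by scheduled study visits in descriptive analyses" and describes the mapping as generally made by "non-overlapping consecutive intervals covering the entire time continuum". The week-50 rows for lipids (> 259) and for vital signs, physical examination and biomarkers (> 176) have no upper limit.

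**OCT analysis set (section 6.2).** It requires a baseline FCT and an FCT "measurement conducted on or after week 40", with no upper limit. Among the supplementary analyses in section 9.5.1: "The primary analysis will be repeated using OAS". The completers set (section 6.3) is drawn from the OAS and separately requires an observed primary endpoint value.

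**Other endpoints.** The section 9.5 table enters NA for sensitivity analyses of the secondary endpoints. For exploratory endpoints, section 9.5.3 says "The analysis will be carried out on observed data and missing data will not be imputed".

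**Link to the protocol.** SAP section 10 states "There are no changes to the protocol-specified analyses". Protocol section 9.1.2 asks for the follow-up scan even outside 50 ± 2 weeks.

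**The concern.** Which values count as observed in the confirmatory test should be fixed before unblinding, and here no sentence fixes it directly. The only closed OCT window is in an appendix that introduces itself as serving descriptive summaries and speaks of covering all of time. At a delayed visit on day 400, the lipid sample would be a week-50 value while the OCT from the same visit would map to nothing.

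The OAS adds to the doubt. A subject scanned only on day 400 belongs to it without having an in-window value, and the SAP does not say whether the OAS repeat uses that value or imputes it.

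Only one of the seven tested endpoints (one primary, six secondary) has an all-scan analysis. Late scans for the other six would enter no analysis, although the protocol asks sites to obtain them.

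If the two readings were equally open, the primary estimate and p-value could depend on a choice made at the time of analysis.

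**Working it through.** **1. Do the cut-offs agree?** Appendix A sets a scheduled day as 7 × week + 1.

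- Week 40: 7 × 40 + 1 = 281, the first day inside (280, 393] and the start of the OAS.
- Week 56: 7 × 56 + 1 = 393, the last day inside the window, so a value after week 56 is one after day 393.

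The COVID-19 paragraph and Appendix A share the upper limit. Appendix A and the OAS share the lower limit. The only numerical mismatch is the missing upper limit in the OAS.

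**2. Which reading fits the text?** The endpoint is change to week 50, and Appendix A is the only place that says which OCT scan is the week-50 scan. The COVID-19 paragraph sets aside an analysis visit window, so one must already apply, and it adds post-week-56 values as something extra.

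- *Late scans missing in the primary analysis:* the COVID-19 analysis adds them back and has a purpose.
- *Late scans observed in the primary analysis:* the COVID-19 analysis repeats the primary, apart from any scan before week 40.

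The second reading empties a pre-specified analysis. The amendment history also says the Appendix A window was widened for week-50 assessments affected by COVID-19, which would be pointless if the window did not bind.

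**3. How late must a scan be?** Protocol tolerance ends at week 52, and 7 × 52 + 1 = 365. The SAP window ends 393 − 365 = 28 days later. Only subjects whose sole follow-up scan falls beyond that are affected.

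**4. Planned power.** Inputs from SAP section 3.2: effect 50.97 µm, SD 86 µm, two-sided alpha 0.05, 150 randomised, 1 in 6 without both scans.

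- Evaluable: 150 × 5/6 = 125.
- Noncentrality at 62 and 63 per arm: 50.97 / (86 × √(1/62 + 1/63)) = 50.97 / 15.38 = 3.31.
- Noncentral-t power: 90.8%, which reproduces the stated 90%.

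**5. What the choice could move.** The late-scan count k is assumed to be 0, 2, 6 or 12. The power column takes k out of 125 and assumes imputation recovers nothing.

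The SD column takes 124 imaged subjects, with lateness unrelated to outcome. The standard error of the effect is 86 × √(4/124) ≈ 15.4 µm. The SD of the difference between the two readings is 86 × √(4/(124 − k) − 4/124). For k = 12 that is 86 × √(0.03571 − 0.03226) ≈ 5.1 µm.

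The last two columns come from 40,000 simulated trials per setting, with an unadjusted t-test and late scans either kept or omitted.

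| k | Power if set to missing | SD between readings (µm) | Significance differs, effect 50.97 µm | Significance differs, effect 30 µm |
|---|---|---|---|---|
| 0 | 90.8% | 0 | 0% | 0% |
| 2 | 90.3% | 2.0 | 1.8% | 4.1% |
| 6 | 89.4% | 3.5 | 3.4% | 7.4% |
| 12 | 87.8% | 5.1 | 5.4% | 10.5% |

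If late scans already sit within the planned 1 in 6, setting them to missing costs nothing against plan.

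**The case for a change.** The strongest contrary case is that a confirmatory analysis should not rest on one adverb in a sensitivity-analysis parenthesis. The sponsor foresaw scans after week 56, and stating the rule would take one sentence.

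**What stands.** The rule is implied, not stated. The Appendix A introduction is looser than its own OCT row. The OAS has no upper limit, so a subject scanned only after day 393 enters the OAS repeat without an in-window value. That repeat is supplementary and is defined as the primary analysis rerun, so the primary window and imputation carry over. The separate completers condition shows that the SAP already allows an OAS member to lack an observed primary value. No confirmatory test uses the OAS.

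**What does not stand.**

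- Different windows for lipids and OCT are a design choice. No planned analysis pairs the two values from one visit, and the appendix says only that the mapping *generally* covers the continuum.
- NA for the secondary endpoints is a stated choice, and they have no rank-based sensitivity analysis either. An all-scan run would be an optional descriptive extra.
- SAP section 10 is not contradicted. Protocol section 10.3.2.2 leaves the imputation detail to the SAP, and defining the week-50 scan is detail of that kind. Asking sites to obtain late scans does not require every one to enter the primary test.

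There is also a positive reason for a window. The last dose is due at week 48, so a scan after week 56 comes more than 8 weeks later. Protocol section 7.1.4 leaves background lipid therapy to the investigator after week 52, and section 3.3.1.1 describes the drug's effects as reversible. Such a scan is a poorer measure of the week-50 state.

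**Conclusion.** This is a gap that analysts would fill sensibly, and it calls for no change to the plan. Sections 8.3, 9.5.1 and 9.5.2 do not state the rule. Appendix A and the COVID-19 paragraph agree on day 393, and only one reading gives the COVID-19 analysis a function: later scans are missing and imputed in the primary analysis and, by the carried-over method, in the secondary analyses. Followed that way, the windowed analysis gives a sound result, and for the primary endpoint the all-scan analysis shows what the late values would have done.

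The size depends on a count the documents do not give. At zero late scans nothing changes. At an assumed 12, power falls from 90.8% to 87.8%, and the two readings differ by an SD of about 5.1 µm against a standard error of about 15.4 µm. These figures assume lateness unrelated to outcome, no information recovered by imputation and an unadjusted t-test in place of the planned ANCOVA.

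The disagreement rates of up to 5.4% at the planned effect and 10.5% at 30 µm describe how often two defensible analyses would part ways. They are not an error rate of the plan. An upper limit for the OAS, tidier Appendix A wording or an all-scan secondary run would be housekeeping. None would correct a wrong result or alter what the trial can conclude.

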3.1 Study Design

This is a phase 3, double-blind, placebo-controlled, randomized study evaluating the effect of evolocumab on coronary atherosclerotic plaques as assessed by OCT at baseline and at week 50 in subjects with an NSTEMI-ACS. The trial duration of 1 year was chosen based on the results of several historical trials. Subjects will be randomized 1:1 into 2 treatment groups no more than 7 days after the signing of the informed consent: evolocumab 420 mg subcutaneously (SC) QM or placebo SC QM. The randomization will be stratified by current statin use (> 4 weeks or ≤ 4 weeks duration) at screening. Investigators will up-titrate statin therapy to the maximally tolerated dose, in accordance with local guidelines, for subjects prior to randomization.

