4.2 Subgroups

Subgroup analysis of the primary endpoint will be conducted for the following subgroups:

Subgroup by stratification factor:

- Current statin use (> 4 weeks or ≤ 4 weeks at the time of screening)

Subgroup by baseline covariates:

- Age (< median, ≥ median; < 65 years of age, ≥ 65 years of age)
- Sex
- Baseline LDL-C (< median, ≥ median)
- Current tobacco use (yes, no)

5. Definitions

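### Treatment interaction with baseline LDL-C and age is tested only on split covariates; if the interaction is linear, a median split discards about 36% of the information for a normal covariate

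*SAP*

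**What the plan says.** SAP 4.2 lists the subgroups for the primary endpoint. LDL-C appears as "Baseline LDL-C (< median, ≥ median"). Age appears as a median split and as a split at 65 years. Statin use (more or less than 4 weeks), sex and tobacco use are the other entries.

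SAP 9.5.1 puts these subgroups into the primary ANCOVA and adds: "Subgroup by treatment interactions will be tested and the p-value of the interaction term will be reported". The same section also enters LDL-C and age unsplit, but only as extra adjustment covariates, one at a time. No product of treatment with either continuous variable is named anywhere.

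Three other places bear on the point:

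- Protocol 10.2.3 leaves its subgroup list open, whereas the SAP 4.2 list is closed.
- SAP 5.3 defines baseline LDL-C as the local laboratory value at screening. Under SAP 3.1, statins are up-titrated before randomization.
- The imputation model in SAP 9.5.1 contains treatment, the stratification factor, baseline LDL-C, baseline minimum FCT and age. It names no interaction.

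**The concern.** The plan uses LDL-C and age as continuous variables for adjustment, then cuts them in two for the interaction test, where information is scarcest. A median split treats subjects just either side of the cut as different and subjects far apart on the same side as alike. The cut-point also depends on the sample.

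The study is sized for the main effect only, so any interaction test is weak. Splitting weakens it further. The interaction p-value is the only result on effect modification that the SAP explicitly commits to, so a null value could be read as evidence of a uniform effect when the test had little chance of showing anything else.

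**Working it through.** **Inputs from SAP 3.1 and 3.2.** "The sample size calculation was performed using a 2-sided t-test with a 0.05 significance level". "This sample size will provide sufficient power (90"%). "the assumed treatment effect is at least 50.97" µm. "The assumed common SD for this study is 86" µm. "Subjects will be randomized 1:1 into 2 treatment groups". "The planned total sample size is 150 subjects", of whom 1 in 6 is expected to lack paired imaging, leaving about 125. The slope is 1.4785 µm of FCT per 1 mg/dL of LDL-C reduction.

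**Input from Protocol 3.3.1.1.** LDL-C lowering was about 60% in an earlier evolocumab imaging study.

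**Assumed, because the documents do not give them.** LDL-C SD of 20 to 40 mg/dL; the shapes of the LDL-C and age distributions; 20% to 50% of subjects aged 65 or over.

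**Step 1, the plan's own figure.** n per arm = 2 × (1.960 + 1.282)² × 86² / 50.97² = 59.8, so 60. With the noncentral t it is 61 per arm, or 122 evaluable, and 122 / (5/6) = 146.4, so 147 randomized. Power with 125 evaluable is 90.8%. The stated 150 and 90% are reproduced. This is power for the main effect; no power or precision is stated for any interaction.

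**Step 2, information kept by a split.** With a linear interaction, the efficiency of a split relative to the continuous term is the squared correlation between the covariate and its split indicator.

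| Covariate and split (distribution assumed) | Efficiency | Loss |
|---|---|---|
| Normal, median | 2/pi = 0.637 | 36% |
| Uniform, median | 0.75 | 25% |
| Lognormal, CV 0.2 to 0.5, median | 0.616 to 0.529 | 38% to 47% |
| LDL-C mixtures truncated at the 60, 80 and 130 mg/dL entry floors, median | 0.705 to 0.576 | 30% to 42% |
| Normal age, cut at 65: 50%, 40%, 30%, 20% aged 65 or over | 0.637, 0.622, 0.576, 0.490 | 36%, 38%, 42%, 51% |

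In the normal case, 0.637 × 125 = 80 subjects.

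**Step 3, what this means for LDL-C.** Suppose evolocumab removes 60% of the baseline value. The treatment effect then rises by 1.4785 × 0.6 = 0.887 µm per mg/dL of baseline LDL-C.

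- Continuous term: SE of the slope = 2 × 86 / (√125 × SDx) = 15.38 / SDx.
- Median split: expected difference between halves = 2 × √(2/pi) × SDx × 0.887; SE = 4 × 86 / √125 = 30.77.
- Power = Φ(estimate / SE − 1.96).

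| LDL-C SD (mg/dL) | z, continuous | Power, continuous | z, split | Power, split |
|---|---|---|---|---|
| 20 | 1.15 | 21% | 0.92 | 15% |
| 30 | 1.73 | 41% | 1.38 | 28% |
| 40 | 2.31 | 64% | 1.84 | 45% |

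Simulation with normal LDL-C (4000 trials per setting) gave 20%, 39% and 61% for the continuous term and 15%, 27% and 42% for the split. Type I error was about 5% for both, so the split buys no extra error control.

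**Step 4, imputation.** If about 1 in 6 endpoints are imputed from a model without the interaction, those subjects contribute almost none of it. If missingness is unrelated to LDL-C, the slope shrinks to roughly 0.887 × 5/6 = 0.74 µm per mg/dL. This affects the split and the continuous term alike.

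**The case against.** The strongest objection is to linearity. Screening LDL-C precedes statin up-titration, and the entry floor is higher for subjects on less statin, so a high value partly marks an untreated patient whose LDL-C the statin will lower in both arms.

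To illustrate, assume that a newly started statin lowers LDL-C by 40% to 55%. A subject on no statin at 130 mg/dL falls to 78 or 58.5. Evolocumab at 60% then removes 46.8 or 35.1 mg/dL, against 36 mg/dL for a high-intensity statin user at the floor of 60. The difference is −0.9 to +10.8 mg/dL, or −1 to +16 µm of FCT. A straight line in screening LDL-C would give 0.887 × 70 = 62 µm. So the pooled relation may be much flatter than Step 3 assumes.

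This stands as a limit on the gain. When statin lowering is applied to the truncated mixtures, the continuous term usually stays the more efficient. The ordering can reverse where the lowering is strong, and power is then low for both tests. A two-group split cannot reveal such curvature, so it is no safeguard against it.

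It also stands that the analysis lies outside the tested hierarchy, that statin-use duration already has an interaction test, and that a null result from a continuous term would still say little.

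A reader might infer that the plan's own LDL-FCT regression predicts an interaction with baseline LDL-C. It does not: SAP 3.2 applies that regression with a flat 50 mg/dL reduction, which implies none. The prediction needs proportional lowering as an added assumption, and nothing in the model concerns age.

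**Conclusion.** The point holds as a low-cost improvement, not as a flaw in the primary analysis. The SAP tests interaction with LDL-C and age on splits only.

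The 36% loss holds for a normal covariate, a median cut and a linear interaction. It should not be read as a property of this trial, because the documents give neither distribution; about 25% to 47% is the range for LDL-C under the shapes tried, and 36% to 51% for the age-65 split. The power figures (21% to 64% continuous, 15% to 45% split) further assume 60% proportional lowering, the plan's slope, an SD of 86 µm and 125 subjects. They would be lower if statin up-titration flattens the relation.

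A reader might also infer that the sponsor intends to claim a uniform effect from a null interaction test. The documents contain no such claim; the risk lies in how a bare p-value may be read.

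**What to change.** In SAP 9.5.1, for baseline LDL-C and for age:

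1. Take the interaction p-value from a treatment-by-continuous-covariate term in the ANCOVA.
2. Report the interaction slope, and the treatment difference with 95% CI at the 25th, 50th and 75th percentiles.
3. Include the same interaction term in the imputation model used for this analysis.
4. Check linearity with a quadratic or spline term, not with the two-group split.
5. Keep the median and age-65 splits for display.
6. State that the analysis is supportive, that the test has low power on either scale, and that a null p-value does not show a uniform effect.

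The cost is a short SAP paragraph and modest programming, including a separate imputation run. It needs no new data and leaves alpha and the testing hierarchy unchanged. Because the subgroup list in Protocol 10.2.3 is open, the protocol wording does not stand in the way. The downside is that a linear form is assumed for a screening LDL-C taken before statin up-titration, which is why item 4 is needed. Fixing the scale before unblinding also avoids a later choice between scales.
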